**Cardiopulmonary Exercise Testing.** Peak  $VO_2$  will be determined at baseline and after 6 months and 1 year on a treadmill using an individualized ramp protocol with collection of continuous ventilatory gas exchange responses. A thorough clinical history, medications and risk factors will be recorded prospectively at the time of baseline exercise testing using computerized forms that include standard definitions of clinical conditions and exercise responses. In accordance with standard practice at the Palo Alto VAHCS, prior to exercise testing, patients complete a questionnaire to estimate exercise capacity; the questionnaire is used to individualize the exercise protocol which allows most patients to reach maximal effort within the recommended range of 8 to 12 minutes (58). We previously observed that this protocol provides the closest relation between measured and estimated metabolic equivalents (METs) (59). Patients will be discouraged from using the handrails for support. Medications will not be changed or stopped prior to testing. A 12-lead electrocardiogram, heart rate, and blood pressure responses will be monitored throughout the exercise test and recovery period. Ventilatory gas exchange measurements will be obtained continuously at rest, throughout exercise, and during 5 minutes of recovery. All subjects will be encouraged to give a maximal effort, and the Borg 6-20 scale will be used to quantify subjective effort (60). Standardized clinical indications for stopping will be used. ST-segment depression will be measured visually at the J junction, and slope will be determined over the following 60 ms and classified as upsloping, horizontal, or downsloping. Ventricular tachycardia will be defined as three or more consecutive premature ventricular contractions, and *frequent* premature ventricular contractions will be defined as 10% or more of the total ventricular contractions. Blood pressure will be measured manually, and exercise capacity will be measured directly using ventilatory gas exchange techniques. The exercise tests will be performed, analyzed, and reported according to a standardized protocol and utilizing a computerized database (61).

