**Quality of Life.** Quality of life will be assessed at baseline, 6-months and 1 year using the standard SF-36 questionnaire (70). The SF-36 provides an 8-scale profile of functional health and well-being scores as well as psychometrically-based physical and mental health summary measures and a preference-based health utility index. This tool has been used in several thousand clinical studies and has proven useful in surveys of general and specific populations, comparing the relative burden of diseases, and in differentiating the health benefits produced by a wide range of different treatments.

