### ***Statistical Analysis Plan***

***Key Question #1:*** Does exercise training favorably alter coronary anatomy and function as determined by non-invasive imaging techniques?

***Statistical Analysis, Key Question #1.*** Myocardial blood flow using PET at rest and following dipyridamole infusion will be expressed as ml flow/100 g/min. The primary outcome, myocardial perfusion reserve, will be calculated as the ratio of the myocardial blood flow during stress (e.g. after dipyridamole) and the myocardial blood flow at rest. Differences within and between groups will be assessed using repeated measures ANOVA, with group (exercise vs. PCI) and test (baseline vs. 1-year) as factors. Post-hoc procedures will be performed using the Bonferonni method.

***Key Question #2:*** Can a program of exercise therapy improve outcomes (exercise capacity, symptoms, repeat hospitalizations, and quality of life) in patients with CAD that are equivalent or superior to PCI?

Statistical Analysis, Key Question #2. These secondary outcomes will include changes in peak  $VO_2$  and other cardiopulmonary exercise test responses (including  $VO_2$  at the ventilatory threshold, exercise time, and heart rate recovery), quality of life measures, and lipid panels. Paired tests will be used (paired t-test or Wilcoxon signed rank test) to compare continuous variables between groups at baseline. Differences between groups after the 1-year study period will be assessed by repeated measures ANOVA, with group (exercise vs. PCI) and test (baseline vs. 1-year) as factors. Post-hoc procedures will be performed using the Bonferroni method.

**Key Question #3:** Will exercise training reduce costs as compared to standard PCI after 1-year?

Statistical Analysis, Key Question #3. Comparison of costs will be made for the individual level change scores using the intervention net-costs (intervention delivery minus healthcare expense cost-savings). Cost effectiveness of the intervention will be defined by the primary outcome at the patient level. That is, changes from baseline in individual global myocardial perfusion reserve using PET at 1-year will be used to calculate the effect. Differences in costs between groups will be assessed using ANOVA.

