### **Sample Size Estimates**

*Sample size estimates are based on our primary endpoint, change in global myocardial blood flow reserve from baseline using pharmacologic stress with dipyridamole, and applying variance in myocardial blood flow reserve measured by PET published previously in subjects with coronary artery disease (71,77,78). We anticipate that the overall change in the primary endpoint will be approximately 15%; this is based on previous measurements of coronary blood flow reserve using PET comparing sedentary and fit subjects cross-sectionally (77), after exercise training (78), and risk reduction interventions such as smoking cessation (96). We also anticipate that these changes will parallel the well-documented changes in exercise capacity with training in subjects with CAD (i.e. mean change in peak  $VO_2 \approx 15\%$ ) (18,19,24). Given a standard deviation of myocardial flow reserve in similar populations of 0.20 ml/g/min both at baseline and after treatment with a pre-post correlation of 0.65 (calculated from the data in reference 96), the standard deviation of the change in myocardial blood flow is 0.167. We want to detect a 15% change (absolute change of  $0.15 \times 0.9$  or 0.135) so the standardized effect size (absolute value of difference in group values for mean change divided by the standard deviation) is about 0.81. Using a 2-sided significance level of 0.05 and 80% power, 25 subjects in each group will be needed to complete the protocol.*

We anticipate that there will be a 20% dropout rate, which is typical of that in the cardiac rehabilitation literature and in accordance with our previous experience. Thus, our target enrollment will be 32 subjects in each group. The dropout rate may be lower given that compliance tends to be better in research studies compared to clinical practice, and that the subjects will receive continuous monitoring, follow-up, and encouragement to remain physically active. *Dropouts will not be included in the statistical analyses (97).*

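### The secondary analyses of exercise-test, SF-36 and lipid outcomes compare only baseline with 1 year in completers, so interim data on subjects who drop out are discarded and avoidable dropout bias is left in

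*Combined protocol and SAP*

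**What the plan says.** Under Statistical Analysis Plan, Key Question #2, the outcomes listed for analysis are peak VO2 and other exercise-test responses, ending with "heart rate recovery), quality of life measures, and lipid panels". The method is: "Differences between groups after the 1-year study period will be assessed by repeated measures ANOVA". The same sentence goes on to define the model's two terms, so that the time term has only two levels: "with group (exercise vs. PCI) and test (baseline vs. 1-year) as factors". Sample Size Estimates expects 20% dropout and adds: "Dropouts will not be included in the statistical analyses".

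The data collected are richer than the data analysed:

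- Cardiopulmonary Exercise Testing: peak VO2 "will be determined at baseline and after 6 months and 1 year on a treadmill".
- Quality of Life: "Quality of life will be assessed at baseline, 6-months and 1 year using the standard SF-36 questionnaire".
- Blood Panels and Table 1: lipids at baseline, 4 months, 8 months and 1 year.

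The plan gives no analysis of these interim visits, no imputation method and no sensitivity analysis for missing data.

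**The concern.** A subject who leaves after the 6-month visit has a baseline and a 6-month exercise test and SF-36 on file, and lipids at 4 months. The stated analysis uses none of them. If subjects who are responding poorly are the ones who leave the exercise arm, the remaining completers look better than the randomised group. The 1-year difference then favours exercise by more than it should. Key Question #2 asks whether exercise gives results equivalent or superior to PCI, so an error in that direction supports the trial's own hypothesis.

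A second, smaller cost is precision. In a two-visit repeated measures ANOVA the group-by-test term is a comparison of mean change scores, which is less efficient than adjusting for baseline. It also cannot use interim values to recover information on dropouts.

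**Working it through.** **Inputs from the documents.** 32 enrolled per arm, 20% dropout, pre-post correlation 0.65 (all from Sample Size Estimates). The 0.65 is given for perfusion reserve; carrying it over to the secondary outcomes is an assumption.

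**Assumptions not in the documents.** Outcome SD of 1 at each visit; correlation 0.65 between baseline and each later visit, and 0.80 between 6 months and 1 year; true 1-year effect 0.80 SD. For the bias check, 10% or 20% of the exercise arm drops out after 6 months, with log-odds rising by 0.5, 1 or 2 for each SD of poorer 6-month change. Dropout in the PCI arm is unrelated to response.

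**The plan's own figure.** SD of change = √(0.20² + 0.20² − 2 × 0.65 × 0.20 × 0.20) = 0.167. Effect size = 0.135 / 0.167 = 0.81. This gives 25 completers per group, and 25 / 0.80 = 31.25, rounded up to 32. The plan's numbers reproduce. On average 32 × 0.80 = 25.6 per arm enter the analysis and 6.4 per arm are excluded.

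**Bias of the completer analysis.** Variance of the 6-month change = 2(1 − 0.65) = 0.70. Covariance of the 6-month and 1-year changes = 0.80 − 0.65 − 0.65 + 1 = 0.50. So each unit by which selection shifts the mean 6-month change shifts the mean 1-year change by 0.50 / 0.70 = 0.71. Simulating the selection in a large sample gives:

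| Exercise-arm dropout | Slope 0.5 | Slope 1 | Slope 2 |
|---|---|---|---|
| 10% | 0.029 SD (3.6%) | 0.054 SD (6.7%) | 0.085 SD (10.6%) |
| 20% | 0.058 SD (7.2%) | 0.103 SD (12.9%) | 0.156 SD (19.5%) |

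Percentages are of the 0.80 SD effect. Predicting the missing 1-year value from baseline and 6 months, as a likelihood model does, leaves a bias below 0.001 SD in every cell. If the 6-month to 1-year correlation is 0.65 instead of 0.80, the covariance is 0.35 and each bias shrinks by 0.35 / 0.50 = 0.7; the 20% row becomes about 0.04, 0.07 and 0.11 SD.

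**Precision of the 1-year contrast (dropout unrelated to response).**

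- Planned change-score comparison: variance = 2 × 2(1 − 0.65) / 25.6 = 0.0547, SE 0.234.
- Completers with baseline as covariate: variance = 2(1 − 0.65²) / 25.6 = 0.0451, SE 0.212. The ratio is (1 + 0.65) / 2 = 0.825, a 17.5% reduction that uses no interim data.
- Adding the 6-month visit: given baseline, the correlation of the 6-month and 1-year values is (0.80 − 0.65²) / (1 − 0.65²) = 0.654, squared 0.427. The further reduction is 0.427 × (1 − 25.6 / m), where m is the number per arm with a 6-month value.
  - No dropout reaches 6 months (m = 25.6): 0%.
  - Half do (m = 28.8): 0.427 × 0.111 = 4.7%.
  - All do (m = 32): 0.427 × 0.20 = 8.5%, SE 0.203.

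With no dropout at all, the interim visit adds nothing to the 1-year contrast.

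**The case against.** The strongest reply is that the harm is conditional and modest. The documents give no reasons for dropout and no rates by arm. Sample Size Estimates says the rate may be below 20% and cites continuous monitoring and encouragement. If the same mechanism works in both arms, the bias largely cancels. Even the largest value, 0.156 SD, is about two thirds of the planned SE (0.156 / 0.234), and the smallest is about one eighth (0.029 / 0.234). This stands, and it is why the bias is given as a range. It does not remove the risk. Subject Burden puts the exercise arm at about 38 hospital visits and the PCI arm at about 8, so equal mechanisms cannot be taken for granted either.

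Three stronger readings are tempting, and the documents do not support them.

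- A reader might credit the whole precision gain to the unused interim visits. Most of it comes from baseline adjustment, which needs no interim data.
- A reader might say that the angina data are likewise analysed at only two visits. Key Question #2 aims to "improve outcomes (exercise capacity, symptoms, repeat hospitalizations, and quality of life", but the Seattle Angina Questionnaire is not in the list of analysed outcomes, and lipids are the only bloods listed. For angina, CRP and HbA1c the gap is an unspecified analysis. The angina schedule also differs: every 3 months in Symptom Questionnaire, but baseline, 6 months and 1 year in Table 1.
- A reader might extend the point to the primary outcome. PET is done only at baseline and 1 year, so there are no interim data to use.

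**Conclusion.** The point holds for peak VO2 and the other exercise-test responses, SF-36 and lipid panels. As written, the plan discards interim data on dropouts and permits a completer bias that could be reduced at no cost in data. The size, about 0.03 to 0.16 SD (4% to 19% of a 0.80 SD effect), rests on dropout confined to the exercise arm and driven by poor 6-month gain, and on the correlations assumed above. It shows what could happen; the documents do not show that it will. The precision gain from the whole change is about 17.5% to 24.6% of variance (the upper figure is 1 − 0.825 × 0.915, using unrounded values), of which the interim visit supplies the part above 17.5%. Because these are secondary outcomes and the planned sample size is unaffected, this is a change that should be made, though the primary result does not depend on it.

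**What to change.** Replace the two-level ANOVA for exercise-test responses, SF-36 and lipids with a mixed model for repeated measures:

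- all scheduled post-baseline visits as responses (6 months and 1 year for exercise tests and SF-36; 4 months, 8 months and 1 year for lipids);
- baseline as covariate, with group, visit and group-by-visit terms;
- every randomised subject with any post-baseline value included, and the dropout exclusion removed for these outcomes;
- the 1-year group difference named as the estimate of interest.

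List the Seattle Angina Questionnaire as an analysed outcome, reconcile its schedule between Symptom Questionnaire and Table 1, and then apply the same model to it.

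The cost is SAP wording; no new visits, subjects or measurements are needed. The limits should be stated with the change: the model assumes that dropout depends on observed data, it protects only subjects who have an interim value, and it leaves the PET analysis as it is.

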### **Sample Size Estimates**

*Sample size estimates are based on our primary endpoint, change in global myocardial blood flow reserve from baseline using pharmacologic stress with dipyridamole, and applying variance in myocardial blood flow reserve measured by PET published previously in subjects with coronary artery disease (71,77,78). We anticipate that the overall change in the primary endpoint will be approximately 15%; this is based on previous measurements of coronary blood flow reserve using PET comparing sedentary and fit subjects cross-sectionally (77), after exercise training (78), and risk reduction interventions such as smoking cessation (96). We also anticipate that these changes will parallel the well-documented changes in exercise capacity with training in subjects with CAD (i.e. mean change in peak  $VO_2 \approx 15\%$ ) (18,19,24). Given a standard deviation of myocardial flow reserve in similar populations of 0.20 ml/g/min both at baseline and after treatment with a pre-post correlation of 0.65 (calculated from the data in reference 96), the standard deviation of the change in myocardial blood flow is 0.167. We want to detect a 15% change (absolute change of  $0.15 \times 0.9$  or 0.135) so the standardized effect size (absolute value of difference in group values for mean change divided by the standard deviation) is about 0.81. Using a 2-sided significance level of 0.05 and 80% power, 25 subjects in each group will be needed to complete the protocol.*

We anticipate that there will be a 20% dropout rate, which is typical of that in the cardiac rehabilitation literature and in accordance with our previous experience. Thus, our target enrollment will be 32 subjects in each group. The dropout rate may be lower given that compliance tends to be better in research studies compared to clinical practice, and that the subjects will receive continuous monitoring, follow-up, and encouragement to remain physically active. *Dropouts will not be included in the statistical analyses (97).*

**Data Management.** All data will be recorded on paper worksheets and entered and maintained in an Access database (Microsoft Corp). This relational database allows storage and manipulation of large data sets and efficient integration of data from multiple sources. Study data will be regularly entered for each participant as they are obtained and error-checking will be performed on an ongoing basis throughout the study. Data will be stored only on VA servers and protected by VA firewalls. Standard security practices will be employed to ensure confidentiality and data integrity. Subject codes will be used in all data files, and identifying information will be kept separately.

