*Measurement of myocardial blood flow will be performed at baseline and 1-year in all subjects. Intravenous  $^{13}\text{NH}_3$  will be used as the flow tracer and serial imaging with PET will be performed (83,84). Measurements will be performed at baseline, and after pharmacologic stress with dipyridamole (85). A 20-minute transmission scan will be acquired first for correction of photon attenuation (86). After the first intravenous injection of  $^{13}\text{NH}_3$  (15 to 20 mCi), resting serial transaxial images will be acquired in a sequence consisting of 12 image frames of 10 seconds, 2 frames of 30 seconds, and 1 frame of 900 seconds. Forty-five minutes later, 0.56 mg/kg of dipyridamole IV will be infused over 4 minutes (85).  $^{13}\text{NH}_3$  (15 to 20 mCi) will be injected 4 minutes after the end of the dipyridamole infusion, and serial images will be recorded in the same sequence. Myocardial blood flow at rest and following dipyridamole infusion will be expressed as ml flow/100 g/min. The myocardial perfusion reserve will be calculated as the ratio of the myocardial blood flow during stress (e.g. after dipyridamole) and the myocardial blood flow at rest.*

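### The sample size uses a 15% change, justified only by non-PCI data, as the exercise-versus-PCI difference; no PCI-arm change is stated and no figure supports a difference that large

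*Combined protocol and SAP*

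**What the plan says.** All references are to the combined protocol and SAP.

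- **Source of the 15%.** Sample Size Estimates says "We anticipate that the overall change in the primary endpoint will be approximately 15" percent, on the basis of PET measurements "comparing sedentary and fit subjects cross-sectionally (77), after exercise training (78), and risk reduction interventions such as smoking cessation (96"). It adds that the change should track the training gain in peak VO2, also about 15%.
- **Use of the 15%.** The same section continues "We want to detect a 15% change", converts this to 0.15 × 0.9 = 0.135, and reports that the "standardized effect size (absolute value of difference in group values for mean change divided by the standard deviation) is about 0.81". With two-sided 0.05 and 80% power this gives 25 completers per group, and 32 enrolled after 20% dropout. No mean change is given for either arm separately.
- **Variance.** The section's starting point is "Given a standard deviation of myocardial flow reserve in similar populations of 0.20 ml/g/min both at baseline and after treatment". Taking the correlation between the two measurements as 0.65, it arrives at an SD of change of 0.167. The variance is attributed to references 71, 77 and 78. The 0.9 has no stated source.
- **Endpoint and analysis.** Under Key Question #1: "The primary outcome, myocardial perfusion reserve, will be calculated as the ratio of the myocardial blood flow during stress" and that at rest, so it has no unit. PET Methods defines it the same way. The test is set out as follows: "Differences within and between groups will be assessed using repeated measures ANOVA, with group (exercise vs. PCI) and test (baseline vs. 1-year) as factors".
- **Expectations for PCI.** The rationale in PET/CTA Study Protocol says that both treatments improve perfusion and that PCI's regional gain shows up globally. It cites a 20% improvement after training (7 patients) and a 20% improvement after PCI, and notes that no randomised trial has established which gives more. It frames the objective as exercise matching PCI.
- **Aims.** Statement of the Problem and Purpose of the Current Proposal make greater improvement than PCI the primary aim. Specific Objectives and Key Question #1 ask whether exercise training improves function, which is a within-arm question.

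**The concern.** The evidence offered for the 15% describes what happens with training, fitness or risk reduction. The calculation uses the number as an advantage over PCI. These are the same quantity only if PCI produces about no change, which the section does not say and the imaging rationale contradicts in direction. If the 15% is instead a target difference, it still needs support as a difference from an active comparator, and no figure in the documents provides it.

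At stake is how the power claim, and later a non-significant primary result, are understood. If both arms improve, the difference could be well below 0.135 and the chance of detecting it much lower than 80%. Because the rationale also speaks of matching PCI and no margin is defined, a null result could be misread.

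**Working it through.** **Inputs (Sample Size Estimates):** SD 0.20 at each time, correlation 0.65, base 0.9, effect 15%, two-sided alpha 0.05, 25 completers per arm, 20% dropout.

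**1. Reproduce the plan's figure.**
- SD of change = √(0.20² + 0.20² − 2 × 0.65 × 0.20²) = 0.1673 (plan: 0.167).
- Effect = 0.15 × 0.9 = 0.135; 0.135 / 0.1673 = 0.807 (plan: about 0.81).
- In a two-group, two-time repeated measures ANOVA, the group-by-test term is equivalent to a two-sample t-test on change. With 25 per arm (48 df), noncentral-t power is 0.798. Solving for n at 0.81 gives 24.9, so 25 per arm.
- Enrolment: 25 / 0.80 = 31.25, so 32 per arm.

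The figure reproduces. A paired, single-arm calculation at 0.81 would need only about 14, so the 0.135 is being used as a between-arm difference, as the section's own definition says.

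**2. Vary the unstated PCI change.** Assumption: exercise gains 15%. The PCI gains are also assumptions. Difference = (15% − PCI gain) × 0.9.

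| Assumed PCI gain | Difference, exercise minus PCI | Standardised | Power, 25 per arm | Power, 32 per arm |
|---|---|---|---|---|
| 0% | 0.135 | 0.807 | 80% | 89% |
| 5% | 0.090 | 0.538 | 46% | 56% |
| 10% | 0.045 | 0.269 | 15% | 19% |
| 15% | 0 | 0 | 5% (2.5% favouring exercise) | 5% |
| 20% | −0.045 (favours PCI) | −0.269 | 15% | 19% |

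With 25 per arm, power is 50% at a difference of 0.0947. That is 0.0947 / 0.9 = 10.5 points, or a PCI gain of 15 − 10.5 = 4.5%.

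**3. Precision.** Expected 95% CI half-width = 2.011 × 0.1673 × √(2/25) = 0.095, or 0.095 / 0.9 = about 10.6% of the base.

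**4. The within-arm question.** A paired t-test of a 0.135 change in 25 exercise completers has 97% power, so this problem does not touch it.

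**5. Units.** The SD is given in ml/g/min, while PET Methods states "The myocardial perfusion reserve will be calculated as the ratio of the myocardial blood flow during stress" and that at rest. A flow unit does not belong to that ratio, so the inputs need confirming before any of these percentages is treated as final.

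**The case against.** The strongest reply is that the 80% is already conditional. The section prints the between-group effect size, about 0.81, and power depends only on that difference, not separately on the PCI change. If 15% is a target difference, a 20% exercise gain with a 5% PCI gain still meets it. This stands in part: the condition is printed, and the losses above are illustrations that assume a 15% exercise gain. It does not supply the missing justification, because the evidence named for the 15% is still all non-PCI.

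A second reply is that training acts on the whole myocardium, so superiority on a global measure is plausible. The protocol does argue this, but only qualitatively.

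Several stronger readings are tempting and are not supported:

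- *The sample size is miscalculated.* It is not; 25 per arm is right for 0.135.
- *The expected difference is zero, because 20% is cited for both treatments.* These come from separate before-and-after studies, one with 7 patients, and the PCI figure is described as perfusion, possibly not reserve. They are too weak to fix a difference.
- *The trial has 46% power.* That needs a 5% PCI gain, a 15% exercise gain, 25 completers per arm and the plan's base and SD. With all 32 completing it is 56%, and the plan allows that dropout may be lower. If the base were 1.35 with the SD of change still 0.167 (an assumption), 10 points would be 0.135 and power would be 80%.
- *80% power exists only if exercise beats PCI by exactly 15 points.* The test is two-sided: the same power applies if PCI is better by that amount, and larger differences give more.
- *The SD is unsourced.* It is attributed to cited studies; only the 0.9 is not.
- *The plan intends to read a null result as similarity.* Nowhere does it say so.

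**Conclusion.** The point holds as a gap in justification. A 15% change supported only by non-PCI evidence is used as the difference from PCI, no PCI-arm change is stated, and the plan's own rationale expects PCI to improve perfusion. No figure in the documents supports a difference of 0.135 in either direction.

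Confidence is high on the missing justification and lower on the exact power losses. Those depend on the assumed gain in each arm, the number of completers, and a base and SD that still need confirming. The point should be fixed; it does not show that the trial must be enlarged.

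**What to change.** In Sample Size Estimates:

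1. State the assumed mean change in each arm and its source, and address the 20% PCI figure cited in the imaging rationale.
2. Restate the power along these lines: *With 25 completers per group, power is about 80% (two-sided 0.05) if the true between-group difference in mean change is 15% of baseline (0.135) in either direction, and less if the difference is smaller.* Add a short table for PCI gains of 0, 5, 10, 15 and 20%, labelled as assumptions.
3. Give the source of the 0.9 base and reconcile the SD's unit with the unitless ratio defined in PET Methods and under Key Question #1. Rerun the table if either input changes.
4. Reconcile the rationale's wording about matching PCI with the primary aim of greater improvement and with the within-arm principal objective. Report the between-group difference with its 95% CI, and state that a non-significant difference does not show similarity because no margin is defined.

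The cost is wording, a check of two inputs and one small table, with no extra patients. The downside is that the stated power looks less favourable. These changes make the claim accurate; they do not raise the power.

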### **PET/CTA Study Protocol**

**Rationale and Accuracy of PET/CTA in the Proposed Study.** *Our objective is to demonstrate that exercise training, an intervention that improves coronary artery endothelial function, can improve myocardial perfusion to a degree that is similar to PCI, an intervention that decreases*

localized vessel obstruction. Both interventions improve myocardial perfusion (see figure), but they have not been previously compared, particularly in a randomized fashion. Myocardial perfusion reserve determined by PET will be the primary outcome measure. It is defined as the ratio of myocardial perfusion during stress to myocardial perfusion at rest. Myocardial perfusion reserve provides information on the functional significance of anatomic stenosis and assesses the ability of the coronary arteries to dilate. It is a well-validated measure of changes in myocardial blood flow both during rest and stress conditions. It has been shown to be a precise correlate of the degree of coronary artery disease, with a predictive accuracy that is superior to other non-invasive techniques (64,71,72). Quantification of myocardial perfusion can be performed with chemical (72-76), exercise (77), or psychological (55) stress, and these methods have been employed to study myocardial blood flow by the investigators of the current proposal. While only a year of training is unlikely to demonstrate changes in coronary atheroma obstruction similar to PCI, it has been shown to improve the ability of arteries to dilate very quickly (ie, within weeks).

A global rather than a regional measure is preferred because a regional method could miss the global improvement in myocardial perfusion associated with exercise training. PCI treats the target lesion; specifically, it lessens the obstruction of the stenotic epicardial artery, resulting in regional flow improvement reflected in global changes. Thus, the most equitable comparison is a measure of overall myocardial perfusion and not just the perfusion of the territory supplied by the stenotic artery.

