In addition, we have chosen myocardial perfusion reserve measured during hyperemia because previous studies have shown improvements in myocardial perfusion reserve following either exercise training (78) or PCI (79), and this type of stress is more convenient and reliable than other stresses. Exercise training, with durations ranging from 4 weeks to 1 year, has been shown to improve coronary endothelial function measured by invasive angiography (19) and myocardial perfusion measured by PET (78). The latter study was a small evaluation of 7 patients using PET perfusion; the investigators reported a 20% improvement in myocardial perfusion reserve after 14 weeks of exercise training. In one study among patients evaluated before and after receiving PCI, a 20% improvement in myocardial perfusion measured by PET was observed (79). However, a randomized controlled trial to determine whether exercise or PCI provides greater improvement in myocardial perfusion has not been performed.

PET perfusion imaging has also been shown to be highly reproducible. In repeat studies of coronary blood flow and coronary flow reserve, the slope of the correlation lines have been shown to be 0.98 and 0.96, respectively, with inter- and intra-observer reliabilities of 0.97 (80). The diagnostic accuracy of PET has been reported in many studies; the table below summarizes the accuracy of PET compared with invasive coronary angiography. Note that the weighted summary shows an overall predictive accuracy of 0.90, higher than other non-invasive methods for detecting coronary artery disease.

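### The sample-size inputs do not fit the unitless stress/rest ratio that is the primary endpoint, so 80% power at 25 per group is not shown for it

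*Combined protocol and SAP*

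**What the plan says.** **Endpoint.** The PET/CTA Study Protocol section names myocardial perfusion reserve as the primary outcome: "It is defined as the ratio of myocardial perfusion during stress to myocardial perfusion at rest". The Statistical Analysis Plan, Key Question #1, repeats that it "will be calculated as the ratio of the myocardial blood flow during stress (e.g. after dipyridamole) and the myocardial blood flow at rest". A ratio of two flows has no unit. Only the component flows carry one: under PET Methods, "Myocardial blood flow at rest and following dipyridamole infusion will be expressed as ml flow/100 g/min". The rationale adds "we have chosen myocardial perfusion reserve measured during hyperemia" and describes reserve as reflecting how well the coronary arteries can dilate.

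**Sample size.** The Sample Size Estimates section says it is built on change in global flow reserve, with variances from three cited PET references (71, 77, 78). Its inputs are:

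- SD: "Given a standard deviation of myocardial flow reserve in similar populations of 0.20 ml/g/min both at baseline and after treatment";
- pre-post correlation 0.65, calculated from reference 96;
- SD of change: "the standard deviation of the change in myocardial blood flow is 0.167";
- target: "We want to detect a 15% change (absolute change of" 0.15 × 0.9, that is 0.135).

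From these it obtains a standardized effect of about 0.81 and 25 completers per group at two-sided 0.05 and 80% power. With 20% dropout, that becomes 32 enrolled per group.

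**The concern.** Three inputs do not belong to a unitless ratio.

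1. The SD carries a flow unit.
2. The derived SD of change is attributed to blood flow, which is a different quantity from reserve.
3. The 15% is taken of 0.9, which has no label, unit or source. As a mean global stress/rest ratio it would put stress flow below rest flow, contrary to the protocol's account of reserve as a hyperemic, dilatory response.

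The documents do not show whether 0.20 and 0.9 describe a flow, a stress-minus-rest difference or something else. This paragraph is the only justification for the size of the trial. If it describes another quantity, the power for the endpoint that will be analysed is unknown, and a non-significant primary result would be hard to interpret.

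**Working it through.** **Inputs (all from Sample Size Estimates).** SD 0.20 at each time point; correlation 0.65; relative difference 15%; base 0.9; two-sided alpha 0.05; power 80%.

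**Step 1. Reproduce the plan.**

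- SD of change = 0.20 × √(2 × (1 − 0.65)) = 0.20 × √0.70 = 0.1673 (stated 0.167).
- Difference = 0.15 × 0.9 = 0.135.
- Effect size d = 0.135 / 0.1673 = 0.807 (stated about 0.81).
- Normal approximation: n = 2 × (1.960 + 0.842)² / 0.807² = 24.1, rounded up to 25 per group.
- Noncentral t: 79.8% power at 25 per group; 26 per group to reach 80%.
- Dropout: 25 / 0.80 = 31.25, rounded up to 32.

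Every stated figure reproduces. The fault lies in what the inputs describe.

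**Step 2. Would deleting the unit repair it?** Keep SD 0.20 and correlation 0.65 as if they were ratio values, and vary the mean ratio. Then d = 0.15 × mean / 0.1673.

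| Assumed mean ratio | d | Power at 25 per group (t) | n per group, t-test | n per group, normal |
|---|---|---|---|---|
| 0.9 | 0.807 | 79.8% | 26 | 25 |
| 1.0 | 0.896 | 87.4% | 21 | 20 |
| 1.5 | 1.345 | 99.7% | 10 | 9 |

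The plan's 25 depends on the 0.9, so relabelling the SD alone leaves the result unexplained.

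**Step 3. When would 25 per group hold for the ratio?** The target is a percentage, so only the ratio's CV (SD/mean) and its pre-post correlation ρ matter:

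d = 0.15 / (CV × √(2 × (1 − ρ))).

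The plan's own pair implies CV = 0.20 / 0.9 = 0.222. The table gives t-test power at 25 per group. The CVs, and the correlations 0.5 and 0.75, are assumptions for illustration; the documents supply none of them for the ratio.

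| CV of ratio | ρ = 0.5 | ρ = 0.65 | ρ = 0.75 |
|---|---|---|---|
| 0.15 | 93% | 98% | over 99% |
| 0.20 | 74% | 87% | 96% |
| 0.25 | 55% | 70% | 84% |
| 0.30 | 41% | 54% | 69% |
| 0.40 | 26% | 34% | 45% |

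**Step 4. Break-even.** Power of 80% at 25 per group needs d = 0.809, so the SD of percent change must be 0.15 / 0.809 = 0.1855. Dividing by √(2 × (1 − ρ)) gives a CV of 0.185, 0.222 and 0.262 for ρ = 0.5, 0.65 and 0.75. For example, with an assumed mean ratio of 2.0 and ρ = 0.65, the SD of the ratio could be at most about 0.222 × 2.0 = 0.44.

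**The case against.** The strongest reply is that a standardized effect is scale-free. SD 0.20 and base 0.9 form a consistent pair, and 25 per group carries over unchanged if the ratio has a similar CV and correlation. Nothing in the documents says that it does not. The section also states that its variances come from published reserve data, so the answer may lie in references 71, 77, 78 and 96, and ml/g/min could be a slip. No loss of power has been demonstrated, and taking 0.20 as a ratio SD with a mean above 0.9 gives more power than stated.

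Much of this stands. The arithmetic is right, no shortfall is shown, and the tabulated CVs are not estimates for this trial. It is also true that ml/g/min and ml/100 g/min differ only by a factor of 100 and do not conflict; what matters is a flow unit set against a ratio.

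What does not stand is the slip as a full explanation. It accounts neither for the 0.9 nor for the SD of change being attributed to blood flow. Citing sources for the variance does not tell the reader what mean and SD of the ratio were used.

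**Conclusion.** The concern holds. The stated effect size, power and sample size are correct consequences of inputs that do not match the endpoint as defined. For the stress/rest ratio, 80% power at 25 completers per group is not shown. This is not a finding that the trial is underpowered. At the plan's correlation of 0.65, power at 25 per group runs from 98% at an assumed CV of 0.15 to 34% at 0.40 and crosses 80% at about 0.22. These figures take 15% as the between-group difference in change, as the plan's own calculation does, and assume equal SDs at both time points. The point should be fixed, because nothing else in the plan supports the number of patients.

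**What to change.** Redo the calculation on the stress/rest ratio, or on its log since the target is a percent change.

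- State the ratio's mean, SD and pre-post correlation without flow units and with a source for each. Use the cited PET references where they report these values; otherwise give explicit assumptions with a range.
- Say what the 0.9 is, or replace it.
- Name the SD of change as that of reserve, not blood flow.
- Restate the power that 25 completers per group give for the primary endpoint, whether above or below 80%.

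The cost is a short recalculation and the rewording of one paragraph. The endpoint, the analysis and the enrolment of 64 can stay as they are.
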